#### **9.4.1            Exposure to Sunlight**

Subjects will take appropriate measures to minimize exposure to UVA/UVB radiation from Day 1 through the final posttreatment Telemedicine Visit. As a precaution, subjects should avoid being in strong direct sunlight and/or UVA/UVB exposure or use protective clothing, broad spectrum sunscreen (UVA + UVB coverage), and sunglasses from first dose until the final posttreatment Telemedicine Visit (Section 9.1.6).

#### **9.5            Prior and Concomitant Medications**

Information regarding prior and concomitant medications, including any AATD medications or therapies, other medications, and herbal and naturopathic remedies, will be collected in each subject's source documentation for medications taken within the 70 days before the first dose of study drug in this study through completion of study participation, as defined in Section 9.1.9.

- Subjects should stop augmentation therapy regimen for at least 42 days prior to level of antigenic AAT sample collection used to determine eligibility, and refrain from restarting augmentation therapy until 28 days after final dose of study drug.
- Subjects may receive doses of prednisone or prednisolone up to 5 mg/day chronically.
- Subjects may receive an acute course of corticosteroids (prednisone, prednisolone, hydrocortisone, or triamcinolone only) as standard of care to treat a PEx (dose and duration per investigator judgement in consultation with the Sponsor).
- Sedation and local anesthesia (e.g., midazolam, fentanyl, local lidocaine) used for the liver biopsy procedure (Group B only) are allowed. Low-dose non-nonsteroidal anti-inflammatory drug (NSAID) pain medications (e.g., acetaminophen with codeine, oxycodone, acetaminophen with oxycodone) are allowed for post-procedure pain. VX-864 may cause increased exposure of sensitive CYP3A4 substrates. When utilizing sensitive CYP3A4 substrates for sedation, local anesthesia, or acute pain management, caution should be utilized and dose adjustments may be considered.

Clinical experience suggests that VX-864 strongly inhibits CYP3A4 and may increase exposure of sensitive CYP3A4 substrates. Therefore, concomitant administration of sensitive CYP3A4 substrates are prohibited (Table 9-1). VX-864 is a mild inhibitor of organic anion transporting polypeptide 1B1 (OATP1B1) and as such use of OATP1B1 substrates are permitted (except when also a substrate of CYP3A4).

#### **9.6            Administration**

##### **9.6.1            Dosing**

There will be no further dosing in this study as of 25 September 2023.

#### **9.7            Dose Modification for Toxicity**

No dose modifications for toxicity are allowed. Treatment may be interrupted as outlined in Section 9.8. If any unacceptable toxicity arises, individual subjects will discontinue dosing (Section 9.1.5).

#### **9.8            Study Drug Interruption and Stopping Rules**

The medical monitor should be notified of an interruption of study drug for any reason and of the resumption of study drug after such interruption.

The investigator has the discretion to discontinue study drug treatment at any time if the investigator feels that the subject's continued participation in the study jeopardizes the subject's safety.

Any subject with worsening of AATD or disease progression that, in the judgement of the treating physician, requires (re)initiation of standard of care treatment (per local guidelines) that is prohibited in this study (including AAT augmentation therapy) will discontinue study drug treatment, and will be discontinued from the study.

Any subject with QTcF values above the threshold values as described in Section 11.6.5 will discontinue study drug treatment.

On Day 1, urine and serum beta-human chorionic gonadotropin ( $\beta$ -hCG) tests will be performed and subsequently every 4 weeks, continuing through completion of study participation, a urine  $\beta$ -hCG test will be performed. If a urine pregnancy test is positive, all study drug dosing will stop, and the pregnancy will be confirmed with a serum  $\beta$ -hCG test. If pregnancy is confirmed, the procedures outlined in Section 11.6.8.2 will be followed.

Study drug treatment may be interrupted for safety concerns at discretion of the investigator.

Study drug administration must be interrupted immediately (before confirmatory testing), and the medical monitor must be notified, if any of the following criteria are met:

- ALT or AST  $>5 \times$  ULN
- Total bilirubin  $>3 \times$  ULN
- ALT or AST  $>3 \times$  ULN associated with total bilirubin  $>2 \times$  ULN and/or clinical jaundice

Subjects with new treatment-emergent ALT or AST elevations of  $>3 \times$  ULN, or total bilirubin  $>2 \times$  ULN, must be followed closely, including confirmatory testing performed within 2 to 3 days of the initial finding and there must be close monitoring of ALT, AST, and bilirubin levels thereafter, as clinically indicated.

If a subject cannot return to the site for confirmatory testing, a local laboratory may be used. Local laboratory results must be reported immediately to the medical monitor, and the subject must have the tests repeated and sent to the central laboratory as soon as possible (ideally within 2 to 3 days).

In subjects who met the interruption criteria listed above, transaminase and/or bilirubin levels must be assessed at a frequency of every 3 to 4 days until the elevations return to normal limits or the subject's baseline levels, whichever is higher, and the subject must be followed closely for clinical progression. A thorough investigation of potential causes must be conducted. The investigation will include (but will not be limited to) the following: clinical chemistry, hematology and coagulation panels as described in Table 11-2 (including bilirubin measured with the BILT3 assay), additional clinical laboratory tests as described in Table 11-4, a liver ultrasound scan, and a consultation with a hepatologist. The liver ultrasound scan, consultation with a hepatologist, and/or other tests may be waived with approval from medical monitor.

- If an alternative, reversible cause of transaminase elevation and/or increased bilirubin has not been identified, study drug must be permanently discontinued.

- If an alternative, reversible cause of transaminase elevation and/or increased bilirubin has been identified, study drug administration may be resumed after transaminases and/or bilirubin return to baseline or are <ULN, whichever is higher. **Approval of the medical monitor is required before resumption of study drug.** Upon resumption of study drug, for the following 2 weeks, transaminases and bilirubin should be monitored every 3 to 4 days, and then weekly for another 2 weeks.

If a protocol-defined transaminase and/or bilirubin elevation interruption threshold recurs, then study drug must be permanently discontinued, regardless of the presumed etiology.

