### **9.1.4        Safety Follow-up**

The Safety Follow-up Visits are scheduled to occur 14 and 28 ( $\pm$  2) days after the last dose of study drug. The Safety Follow-up Visit assessments are listed in Table 3-4.

The Safety Follow-up Visits are required for all subjects.

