### **9.1.5        Early Termination of Treatment**

If a subject prematurely discontinues study treatment, an ETT Visit should be scheduled as soon as possible after the decision to discontinue study drug treatment. Subjects who prematurely discontinue study drug treatment will also be required to complete the Safety Follow-up Visits, approximately 14 and 28 ( $\pm$  2) days after their last dose of study drug.

If the ETT Visit occurs 3 weeks or later following the last dose of study drug, then the ETT Visit will replace the Safety Follow-up Visits, and a separate Safety Follow-up Visit will not be required. The ETT visit may be performed at the site or by telephone or video.

If a subject withdraws consent for the study, no further assessments will be performed. Vertex may retain and continue using the study data and samples after the study ends, and may use the samples and information in the development of the study compound, for other drugs and diagnostics, in publications and presentations, and for education purposes. If a subject withdraws from the study (Section 9.9), the study data and samples collected will remain part of the study.

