### **9.1.9 Completion of Study Participation**

Completion of study participation for each individual subject is defined as one of the following:

- For subjects who complete the Treatment Period: the last Safety Follow-up Visit.
- For subjects who prematurely discontinue study drug treatment but do not withdraw consent, the latest of the following: the Week 48 Visit, ETT Visit, or the last Safety Follow-up Visit (if required), or the last posttreatment Telemedicine Visit.
- For subjects who withdraw consent: the date of withdrawal of consent (Section 9.9).

If subjects are lost to follow-up (Section 9.1.8), the date of completion of study participation will be defined as the date of last contact.

The end of study is defined in Section 13.2.9.

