## 9.9 Removal of Subjects

Subjects may withdraw from the study at any time at their own request. Subjects may be withdrawn from study drug treatment at any time at the discretion of the investigator or Vertex for safety, behavior, noncompliance with study procedures, or administrative reasons. If a subject has been withdrawn from study drug treatment, the reason for withdrawal should be documented and every effort should be made to continue to follow the subject until the end of the study.

In addition, a subject must be discontinued from study drug treatment if the subject meets any of the following criteria:

- Has a screening PiZZ genotype from the central laboratory that does not confirm study eligibility after a historical PiZZ genotype or was used to establish eligibility. These subjects must be discontinued from the study (Section 8.1).
- Meets any of the stopping (discontinuation) criteria (Section 9.8)
- Becomes pregnant (the subject or the female partner of a male subject; Section 11.6.8.2)

If a subject does not return for a scheduled visit, reasonable effort will be made to contact the subject. In any circumstance, reasonable effort will be made to document subject outcome. The investigator will inquire about the reason for withdrawal, request that the subject return all unused investigational product(s), request that the subject return for a Safety Follow-up Visit, if applicable (see Section 9.1.5), and follow up with the subject regarding any unresolved AEs.

If a subject withdraws consent for the study, no further assessments will be performed. Vertex may retain and continue using the study data and samples after the study ends and may use the samples and information in the development of the study compound, for other drugs and diagnostics, in publications and presentations, and for education purposes. If a subject withdraws from the study, the study data and samples collected will remain part of the study. A subject will not be able to request the withdrawal of his/her information from the study data. A subject may request destruction of the samples collected from him/her during the study as long as those samples can be identified as his/her samples.

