### **13.1.1.3 Documentation of Adverse Events**

All AEs will be collected from the time the ICF is signed until the following times:

- For subjects who do not enroll: time of screen failure (e.g., screen failure, withdrawal of consent)
- For enrolled subjects: completion of study participation, as defined in Section 9.1.9

All subjects will be queried, using nonleading questions, about the occurrence of AEs at each study visit. When possible, a constellation of signs and/or symptoms will be identified as 1 overall event or diagnosis. All AEs for enrolled subjects will be recorded in the CRF and source document. AEs for subjects who are screened but not subsequently enrolled will be recorded only in the subject's source documents. The following data will be documented for each AE:

- Description of the event
- Classification of "serious" or "nonserious"
- Date of first occurrence and date of resolution (if applicable)
- Severity
- Causal relationship to study drug(s)
- Action taken
- Outcome
- Concomitant medication or other treatment given

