9 STATISTICAL ANALYSIS

9.1 General Considerations

The Schedule of Assessments is provided in Section 3 of CSP. The precision standards for reporting safety variables are provided in an internal Biometrics document that specifies the programming rules including the precision for derived variables.

Continuous variables will be summarized using the following descriptive summary statistics: the number of subjects (n), mean, SD, median, minimum value (min), and maximum value (max).

Categorical variables will be summarized using counts and percentages.

Baseline value, unless specified otherwise, will be defined as the most recent non-missing measurement (scheduled or unscheduled) collected before the first dose of study drug. For ECGs, the baseline value will be defined as the average of the non-missing pretreatment measurements (triplicate) on Day 1. For subjects who have ever been on augmentation therapy at any time, only functional and antigenic AAT levels collected during screening >42 days after the last dose of augmentation therapy can be used to define baseline values.

Change (absolute change) from baseline will be calculated as post-baseline value – baseline value.

Treatment-emergent (TE) Period will include the time from the first dose of study drug to 28 days after the last dose of study drug or to the completion of study participation (as defined in Section 9.1.8 of CSP), whichever occurs first.

Visit Window: The analysis visit windows for the protocol-defined visits are provided in Appendix A.

Unscheduled visits: Data obtained from unscheduled visits will be included in the analysis as follows:

- In scheduled visit windows per specified visit windowing rules
- In the derivation of baseline and last on-treatment measurements
- In the derivation of maximum and minimum values during TE period, and maximum and minimum change from baseline values during TE period for safety analyses
- In individual subject data listings as appropriate

Incomplete or missing data will not be imputed, unless specified otherwise.

Outliers: No formal statistical analyses will be performed to detect and/or remedy the presence of statistical outliers, unless specified otherwise.

All individual subject data will be presented in individual subject data listings based on the All Subjects Set.

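### Protocol 9.8 takes a subject who needs augmentation therapy out of the study, other sections keep that subject in follow-up, and the SAP has no rule for AAT drawn after a restart

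*Protocol*

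**What the plan says.** **Leaving the study.** Protocol 9.8 concerns worsening AATD or disease progression that, in the treating physician's judgement, needs standard-of-care treatment "that is prohibited in this study (including AAT augmentation therapy) will discontinue study drug treatment, and will be discontinued from the study".

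**Staying in follow-up.**
- Protocol 9.1.4: "The Safety Follow-up Visits are required for all subjects".
- Protocol 9.1.5: "Subjects who prematurely discontinue study drug treatment will also be required to complete the Safety Follow-up Visits", at about 14 and 28 days after the last dose.
- Protocol 9.9, on subjects withdrawn from study drug: "every effort should be made to continue to follow the subject until the end of the study". It lists the 9.8 criteria as reasons to stop study drug. It repeats removal from the study only for a genotype that the central laboratory does not confirm.
- Protocol 9.1.9, on when participation ends: "For subjects who prematurely discontinue study drug treatment but do not withdraw consent, the latest of the following: the Week 48 Visit, ETT Visit", the last Safety Follow-up Visit if required, or the last telemedicine visit. It has no entry for a subject removed under 9.8.

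**Restarting augmentation.** Protocol 9.5 tells subjects to "refrain from restarting augmentation therapy until 28 days after final dose of study drug", and Table 9-1 sets the same limit. Neither says whether this holds for a 9.8 subject.

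**SAP.** Section 9.1 accepts only screening AAT values taken more than 42 days after the last augmentation dose as baseline, and gives no matching rule after baseline. Table 12-1 makes both Safety Follow-up visits efficacy visits, assigned by nominal visit. Section 9.3.2 summarizes observed AAT and its change from baseline at each visit, by group and overall. Section 9.2.1 counts a subject as a study completer on a Safety Follow-up or telemedicine visit, and lists study discontinuation separately.

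**The concern.** The protocol does not say in one voice whether a 9.8 subject attends the follow-up visits. If the subject does attend, the AAT samples may reflect infused AAT as well as any remaining effect of VX-864. The SAP recognises that problem for baseline and leaves it open for follow-up. A reader of the Day 14 or Day 28 Safety Follow-up row would take the mean as an off-drug level, with nothing to show that a value came from a subject on augmentation. The disposition table could also place one person in two categories that ought to be alternatives.

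This deserves attention because dosing stopped on 25 September 2023, so follow-up is the main study activity left, and Section 9.3.2 reports AAT descriptively at each of those visits.

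**Working it through.** The plan gives no figure on this point, so the check compares passages and then adds simple arithmetic.

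**1. Do the passages agree?** For a 9.8 subject who has not withdrawn consent:

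| Question | Protocol 9.8 | Other sections |
|---|---|---|
| Still in the study after stopping drug? | No | Yes: 9.9 asks for follow-up to study end |
| Safety Follow-up Visits held? | Silent | Yes: 9.1.4 and 9.1.5, no exemption |
| When does participation end? | Silent | 9.1.9: latest of several visits |
| Restart of augmentation | Foreseen as required | 9.5 and Table 9-1: not until 28 days after last dose |

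No sentence ranks 9.8 above or below the others.

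**2. When could a follow-up sample be drawn on augmentation?** The visits fall 14 and 28 (±2) days after the last dose, so the windows are Days 12–16 and 26–30, which is 5 + 5 = 10 days. Window days on or after a restart on Day r:
- r = 12 or earlier: 5 + 5 = 10
- r = 14: 3 + 5 = 8
- r = 20: 0 + 5 = 5
- r = 28: 0 + 3 = 3

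These are calendar days, not samples; each subject has two scheduled draws. A subject who complies with 9.5 can restart from about Day 28 at the earliest. That subject is exposed only if the Day 28 sample is taken after the restart, within Days 28–30. The larger counts need a 9.8 case or a deviation.

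**3. Does the SAP screen such a sample out?** Table 12-1, note 3, closes the on-treatment efficacy windows one day after the last dose of study drug. That largely protects the on-treatment visits. The follow-up visits are assigned first, by nominal visit, and are not screened for augmentation.

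**4. Size of the AAT effect.** Let X be the amount by which augmentation raises one subject's value. The visit mean shifts by X/n. X is not in the documents, and neither is the actual n at follow-up. For scale only, assume X from 5 to 21.5 µM. The upper end is the functional assay ceiling minus the planned baseline mean, 25.6 − 4.1 = 21.5. Use the planned n of 10 (one group) and 20 (overall):

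| Assumed X (µM) | X/10 | X/20 |
|---|---|---|
| 5 | 0.50 | 0.25 |
| 10 | 1.00 | 0.50 |
| 15 | 1.50 | 0.75 |
| 21.5 | 2.15 | 1.075 |

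These are illustrations, not estimates. If the subject is removed instead, the shift is 0 and n falls by 1.

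**5. Disposition.** A 9.8 subject who attends a Safety Follow-up Visit satisfies the completer definition in SAP 9.2.1 and is also a study discontinuation. One subject is 1/20 = 5 percentage points of the planned total.

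**The case against.** The best reply is that the protocol largely answers the follow-up question. The synopsis and Section 9.1 require the visits for everyone. They then deal expressly with subjects who end participation early: an ETT visit replaces follow-up only when it falls 3 weeks or more after the last dose. SAP 7.1 is similar. Only withdrawal of consent stops assessments (9.1.5, 9.9). On this reading, leaving the study under 9.8 does not cancel the visits. That weight of text does favour follow-up. It does not remove the difficulty, because nothing ties it to 9.8, and holding the visits is exactly what brings augmented values into the SAP summaries.

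A reader might infer that adverse-event data are lost as well. AE collection runs until "For enrolled subjects: completion of study participation, as defined in Section 9.1.9", and the SAP's TE Period runs "to 28 days after the last dose of study drug or to the completion of study participation (as defined in Section 9.1.8 of CSP". If a 9.8 exit ended participation, both would close early. The documents do not support this. The second entry in 9.1.9 already covers a subject who stops drug without withdrawing consent, and no passage ends participation on the date of a 9.8 exit.

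A reader might also think that the SAP's reference to CSP 9.1.8 changes the TE Period. That section is Lost to Follow-up and does not contain the general definition of completion. Protocol 12.3.1 gives the same TE definition and cites 9.1.9. The slip is clerical.

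It also stands that the output is descriptive, that no restart is documented, and that with all dosing stopped the 9.8 rule has no further dosing to stop. Part of the SAP is blacked out, including most of 9.3.1 on the primary analysis, so what the SAP settles is judged on the visible text only.

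**Conclusion.** The concern holds in limited form and is minor: a cheap improvement. Protocol 9.8 is not reconciled with 9.1.4, 9.1.5, 9.1.9, 9.9 and 9.5. If the visits are held as most of the text requires, the SAP has no way to separate follow-up AAT drawn on augmentation from follow-up AAT drawn off it.

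The effect reaches descriptive AAT summaries at two follow-up visits and the disposition counts. One value shifts a visit mean by X/n, with X unknown. The number of affected subjects is not given and may be zero. The planned Week 48 half-width of 0.59 to 1.24 µM is not a useful yardstick: it was computed for 16 evaluable subjects at Week 48, not for follow-up means.

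No effect on the primary endpoint is claimed, and no loss of TE Period or AE collection. A reader might infer either, but the visible text supports neither.

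**What to change.** 1. **Protocol.** Reconcile 9.8 with 9.1.4, 9.1.5, 9.1.9, 9.9 and 9.5/Table 9-1, so that they give one answer on whether the follow-up visits are held and when participation ends. Which clinical rule should apply is for the sponsor and investigators, not this review.
2. **SAP 9.3.2 and Appendix A.** Flag functional and antigenic AAT values drawn after any post-baseline augmentation dose. Show the by-visit summaries with and without them, and report the number flagged at each visit. The dates are already collected under Protocol 9.5.
3. **SAP 9.2.1.** Define completing and discontinuing the study so that a subject can fall in only one.
4. **SAP 9.1 (editorial).** Change the TE Period reference from CSP 9.1.8 to 9.1.9.

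The cost is a protocol clarification, three short SAP edits and a check against medication dates. If any value is flagged, there is one extra version of the AAT summaries. If none is, no output is added.
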